#### 4.4.7 Exercise Training Intervention

TBI participants will be block randomized to one of 3 exercise training regimen for 12 weeks. All exercise training interventions will be supervised and performed 3 times per week, for 45 minutes each session at the NIH Clinical Center. All women of childbearing potential randomized to either exercise group will perform monthly pregnancy testing. The specific exercise intervention is as described below:

#### A. Aerobic exercise training (AET)

Subjects will perform physical exercise on an elliptical trainer, with emphasis on aerobic exercise being performed at a target heart rate (HR) range for 30 minutes. The target HR will be calculated as a range of between 70% and 80% of the heart rate reserve (HRR); where HRR = 0.70 to 0.80 \* (peak HR – resting HR) + resting HR. The session will also include 15 minutes of warm-up and cool-down at sub-training intensity. Aerobic exercise will be continuous over the 30 minutes unless the patient cannot tolerate the regimen continuously. If the training regimen cannot be tolerated, exercise bouts will be alternated with rest intervals until the total time of 30 minutes of exercise at the target HR is achieved. The primary goal of this type of exercise is to increase the intensity at which the target HR is achieved. This would be achieved by preferentially increasing the resistance on the elliptical trainer, rather than speed. Subjects in AET would be exercising at ~ 70 to 80% of maximal VO2. A paper-based log sheet will be used to record the heart rate, resistance and speed used in each session (Appendix 9).

#### B. Rapid-resistive exercise training (RET)

Subjects will perform physical exercise on an elliptical trainer, with emphasis on maintaining a near maximal speed of movement for 30 minutes. The session will also include 15 minutes of warm-up and cool-down at a slower speed. Subjects will be encouraged to progressively increase their maximal speed over time, while maintaining a smooth rhythm throughout the session. Once the subject has reached a speed of 80 RPM, resistance will be added. It will be increased incrementally as long as adding resistance does not decrease their speed below 80 RPM and does not increase their heart rate beyond the target set for moderate exercise as described below. Rapid-resistive exercise will be continuous over the 30 minutes unless the patient cannot tolerate the regimen continuously. If the training regimen cannot be tolerated, exercise at near maximal speed of movement is achieved. The primary goal of this type of exercise is to increase movement speed and reciprocal coordination, while being within moderate intensity. Subjects in

RET would be exercising below their anaerobic threshold (determined from the CPET), which is typically about 50% HRR and maximal  $VO_2$ . Therefore, the heart rate associated with ~85% of each subjects' anaerobic threshold would be determined and this target heart rate would not be exceeded during their exercise sessions to ensure exercise is of moderate intensity. A paper-based log sheet will be used to record the heart rate, resistance and speed used in each session (Appendix 9).

Subjects in the exercise training group will complete at least 30 of the 36 training sessions in twelve weeks to remain eligible for the study. Subjects will wear a heart rate monitor during the sessions such that beat by beat heart rate is displayed continuously. The frequency of the sessions will be three times per week, unless make up sessions are needed to adhere to the minimum sessions required. Sessions will be supervised by credentialed RMD personnel.

Subjects randomized to the wait-list control will be further randomized to either AET or RET after Assessment Visit 2. In the first 3 months, subjects in the wait-list control will receive no exercise training; however they will be contacted monthly to ensure compliance and to maintain contact (Appendix 10). For subjects initially randomized to either AET or RET, they will no longer follow a formal exercise intervention at NIH following Assessment Visit 2. However, they will be contacted monthly for the next 3 months and asked about their weekly physical activities (Appendix 10).

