#### Lead Associate Investigator

[name]	RMD/CC	[name]	[contact]	[contact]
----------------	--------	---------------	--------------	-------------------

Human Research Protections Program Investigator and Staff Training:

For this protocol, the following "Just in time" human subjects protection training courses are required for investigators and staff: None

Total requested accrual: 100 subjects (80 TBI Patients and 20 healthy volunteers)

N = 26 Wait-list control

N = 27 Aerobic Exercise Intervention

N = 27 Rapid-Resistive Exercise Intervention

N = 20 Healthy Volunteer Controls

Project Uses Ionizing Radiation: Medically-indically-i	No [ ated only d only	☐ Yes (attach RSC/RDRC documentation)
IND/IDE Drug/Device/#	🗵 No	$\Box Yes (attach FDA documentation)$
Sponsor:		
Durable Power of Attorney	🗵 No	□ Yes
Multi-institutional Project	□ No	X Yes

Institution#1: Center for Neuroscience and Regenerative Medicine FWA #\_ A00001628\_\_\_\_\_ Date of IRB approval September 15, 2016 (attach IRB documentation)

Institution#2: Department of Veterans Affairs Medical Center, Washington DC FWA # A00002475\_\_\_\_\_ Date of IRB approval January 19, 2018 (attach IRB documentation)

Data and Safety Monitoring Board □ No ⊠ Yes - Monitor

[name]		
University Sports Medicine		
State University of New York at Buff	falo	
[name]		
Office [contact]		
e-mail: [contact]		
Technology Transfer Agreement Agreement type and number Collaboration agreement with DC	□ No CVAMC Expir	☑ Yes – see Appendix 12 ration Date4/19/2022_
Samples are being stored	□ No	🗵 Yes

Flesch-Kincaid reading level of consent form: 10.0

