This assessment visit will last approximately 8 hours, including time for rest and meals, and may be performed within one day or over the course of several days within a 4 week period. Upon completion of all baseline assessments, patients will be block randomized to one of three groups: 1) a waitlist control, 2) an exercise intervention consisting of exercise at vigorous intensity (Aerobic exercise training group, AET), or 3) an exercise intervention consisting of exercise at moderate intensity (Rapid resistive exercise training group, RET). Both training interventions will be performed 3 times a week for 12 weeks, with a session duration of approximately 1 hour. After 12 weeks, all patients will repeat the same assessments performed at baseline (3 month follow-up). Patients in the control group will then be randomized to either AET or RET, while patients in the exercise training groups will cease their formal supervised exercise training regimen. All patients will return after 12 weeks to perform their final assessment visit (6 month follow-up).

All assessments and training interventions are outpatient visits and will occur at the NIH Clinical Center in the Rehabilitation Medicine Department.

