### 4.5 Relationship to other protocols

Potential participants do not have to enroll or participate in any other protocol in order to participate in this study.

This study is related to a number of other protocols and projects. The Center for Neuroscience and Regenerative Medicine (CNRM) is a collaborative intramural federal program involving the United States Department of Defense (DoD) and the National Institutes of Health (NIH). It joins clinicians and scientists across disciplines to catalyze innovative approaches to traumatic brain injury (TBI) research.

The Uniformed Services University of Health Sciences (USUHS) heads the operation of the CNRM (www.usuhs.mil/cnrm).

CNRM initially provided Henry Jackson Foundation staff and equipment to NIH through a CRADA. These staff included several providers who perform the assessment instruments. All providers are credentialed at the Clinical Center for work at NIH.

The CNRM Informatics Core was created to store all imaging and clinical data from CNRM-related protocols. All clinical data will be coded and have personally identifying material removed prior to transfer to CNRM.

Research data from neuropsychological assessments, balancing and imaging performed within the past 3 months under other CNRM studies may be included as baseline assessments in this study. This is to avoid patient burden and practice effects. Research data from the same subject may also be shared directly with CNRM investigators in protocol 10-CC-0118 (Long-term Clinical Correlates of TBI: Imaging, Biomarkers and Clinical Phenotyping Parameters) and 11-N-0084 (Evaluation and Diagnosis of Potential Research Subjects with Traumatic Brain Injury).

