# 9. Statistical Analysis

### 9.1 Analysis of data

The primary analysis is a mixed model (with time as the within-subject factor and exercise group as the between subject factor) analysis of variance (ANOVA) which will be used to determine significant differences in the primary (ANOVA) and secondary outcome variables (MANOVA by outcome category – i.e. motor, cognitive, behavioral, etc – to help control for multiple comparisons) as a result of exercise. Therefore, the data will include the time points immediately pre and post exercise for all subjects. We are interested in both main effects for time and exercise as well as potential interaction effects between exercise group and time.

All subjects completing the protocol and not withdrawing or presenting off study criteria will be included in the analyses. Secondary analyses related to protocol adherence and other aspects of feasibility are anticipated. Estimation of the necessary and sufficient sample size was calculated for a large effect change in the main outcome variable, pre- to post-training change in executive functioning. Significance will be set at p < 0.05.

While we do not anticipate that subjects will improve over time in the absence of exercise, we have included a waitlist control to evaluate this, and we will compare the amount of change over time in the control group versus the exercise group that were not waitlisted using an independent t-test. Also for the exercise group that was not waitlisted, there will be a three month follow up period evaluated to determine whether there is any change compared to the end of the exercise period using paired t-tests.

The change in aerobic capacity and fast elliptical speed will be correlated with changes in the other outcomes measures. Baseline dopamine transmission scores will also be correlated with all motor outcomes using linear regression.

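### The primary ANOVA pools AET and RET subjects from two separate randomisations with no stage term: a small loss of power, and a small bias only if the stage mix ends up unequal

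*Combined protocol and SAP*

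**What the plan says.** **Two allocations.** After baseline, "patients will be block randomized to one of three groups" (section 4.1): waitlist, AET or RET. The accrual list on the cover page gives "N = 26 Wait-list control", "N = 27 Aerobic Exercise Intervention" and "N = 27 Rapid-Resistive Exercise Intervention". Section 4.4.7 then states: "Subjects randomized to the wait-list control will be further randomized to either AET or RET after Assessment Visit 2". No ratio is given for this second allocation. Section 4.4.8 describes blocking to keep group sizes level, without saying whether the second allocation is blocked separately.

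**One model.** Section 9.1 makes a mixed ANOVA the primary analysis, "with time as the within-subject factor and exercise group as the between subject factor", and adds: "Therefore, the data will include the time points immediately pre and post exercise for all subjects". For direct subjects that pair is Visits 1 and 2; for delayed starters it is Visits 2 and 3. Only the control t-test and the follow-up paired t-tests are limited to exercisers who were never waitlisted, so pooling in the ANOVA looks intended. No stage, period or sequence term is named.

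**Retest gains.** Section 4.5 mentions practice effects when explaining why recent assessments from related studies may serve as baseline: "This is to avoid patient burden and practice effects". Section 9.1 says no improvement is expected without exercise, and that the waitlist is there to check this.

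**Who is analysed.** Section 9.1 analyses completers. Section 3.1 aims for at least 20 per group at the second assessment visit. Section 7.3 promises to replace withdrawals. Section 9.2 expects about one-third attrition.

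**The concern.** AET and RET are randomised against each other within a stage, not across stages. A delayed starter's pre-exercise score is the second exposure to Trail Making Test B (TMT-B) rather than the first. It comes three months later, and only from people who stayed through the wait. The average pre-post change could therefore differ between stages for reasons unrelated to exercise type.

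The contrast at stake is AET against RET, which is the group-by-time term in this ANOVA and bears on the primary objective in section 2 (the effect of exercise intensity on cognition). If the stage gap is left out of the model, it goes into the residual. If the two arms also finish with different proportions of delayed starters, part of the gap goes into the AET-RET estimate.

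**Working it through.** **The plan's own figure.** Section 9.2 gives 20 subjects per condition. It cannot be reproduced, because no pilot mean or SD for TMT-B is stated. It is used here only as a completer count.

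**Inputs from the plan.** 20 direct completers per arm (sections 3.1 and 9.2). If 20 waitlist subjects also reach Visit 2 and are split 1:1, there are 10 delayed starters per arm.

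**Assumptions, not in the documents.** A 1:1 second allocation; a two-sided 5% test; a true AET-RET difference of 0.75 SD of change; a stage gap g in average change of 0.2, 0.5 or 0.8 SD. All SDs are within-stage SDs of the pre-post change. With two time points, the group-by-time test is equivalent to a two-sample t-test on change.

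**Step 1: equal mix, 20+10 in each arm.** The delayed share is p = 10/30 = 1/3. Ignoring stage multiplies the SD of change by √(1 + p(1−p)g²) = √(1 + (2/9)g²). Power comes from simulating change scores with and without a stage term.

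| g (SD) | SD factor | Power without stage | Power with stage |
|---|---|---|---|
| 0.2 | 1.004 | about 81% | about 82% |
| 0.5 | 1.027 | about 80% | about 81% |
| 0.8 | 1.069 | about 77% | about 81% |

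The with-stage figure does not truly depend on g; the move between 81% and 82% is simulation error and rounding. Bias is zero. Without the term, type I error is about 4.5% at g = 0.5 and about 3.5% at g = 0.8, so the test is valid but conservative.

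**Step 2: unequal mix, 20+10 against 20+6.** Bias in the AET-RET estimate is g times the difference in delayed shares:

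- share difference = 10/30 − 6/26 = 0.333 − 0.231 = 0.103
- g = 0.2: 0.2 × 0.103 = 0.02 SD
- g = 0.5: 0.5 × 0.103 = 0.05 SD
- g = 0.8: 0.8 × 0.103 = 0.08 SD

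Its direction depends on which arm has more delayed starters and on which stage improves more. With the stage term, simulated bias is about zero and type I error is about 5%.

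**Step 3: how much differential loss that takes.** From 10 and 10 delayed starters, it means losing none in one arm and 4 of 10 in the other. If all 26 waitlisted subjects were re-randomised 13 and 13, it means losing 3 (23%) and 7 (54%).

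**Step 4: price of the term if there is no stage gap.** The information on the AET-RET difference is n₁n₂/(n₁+n₂).

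- Equal mix: unadjusted 30×30/60 = 15; within-stage 20×20/40 + 10×10/20 = 10 + 5 = 15. Nothing is lost except the degree of freedom.
- 20+10 against 20+6: unadjusted 30×26/56 = 13.93; within-stage 20×20/40 + 10×6/16 = 10 + 3.75 = 13.75. The standard error grows by √(13.93/13.75) − 1, or about 0.6%.

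**Step 5: precision within the delayed stage alone.** With 10 against 10, the 95% half-width is 2.10 × √(2/10) = 0.94 SD.

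**The case against.** The strongest reply is that the plan gives little reason to expect a stage gap. Practice effects appear only as a reason for reusing recent assessments, and section 9.1 expects no change without exercise. Nothing says the gain from test 1 to 2 differs from that from test 2 to 3. This stands: g is purely an assumption, and at small g the stage term changes almost nothing.

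Second, blocking and the replacement promise work against an unequal mix, and with a balanced mix, omitting a prognostic factor costs efficiency rather than validity. This also largely stands. However, section 3.1's target stops at Visit 2, before delayed starters exercise. Section 7.3 does not say whether a replacement would enter at the stage where the loss occurred. The analysis set is completers only. An unequal mix is therefore less likely, but not excluded.

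Third, section 8.1 defines the primary outcome against the control group, and the levels of exercise group in the ANOVA are not spelled out. The control comparison has its own t-test, on concurrent Visit 1-2 data from subjects who were not waitlisted, and it is unaffected. The point is confined to AET versus RET.

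A reader might infer something stronger: that the protocol itself predicts practice effects that bias the intensity comparison, or that the test produces excess false positives. The documents do not support that. They predict no stage difference, there is no bias when the mix is equal, and in that case the test rejects too seldom rather than too often. Scenarios that leave fewer than 20 direct completers in an arm also conflict with the section 3.1 commitment.

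**Conclusion.** The gap in the model is real and its consequences are small. AET versus RET is randomised in two stages, and the primary ANOVA has no term for stage. With an equal mix, the cost is about 1 percentage point of power at a stage gap of 0.2 or 0.5 SD and about 4 points at 0.8 SD. With completers at 20+10 against 20+6, the AET-RET estimate shifts by about 0.02 to 0.08 SD over the same range. These sizes rest on the assumed gap, a 0.75 SD effect, a 1:1 second allocation and the completer counts used; only the 20 per condition comes from the plan. The point does not touch the control comparison. Severity is minor and confidence moderate. It is worth making because the remedy costs almost nothing and is more credible if fixed before results are seen.

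**What to change.** In section 9.1, add randomisation stage (at entry, or after the waitlist period) and stage-by-time to the mixed ANOVA for TMT-B, and the same terms to the secondary-outcome models. AET and RET are then compared within each stage and the two comparisons pooled. If stage-specific AET-RET estimates are shown, label them descriptive, since about 10 per arm in the delayed stage is too few to interpret.

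The cost is a sentence in the plan and one or two degrees of freedom, with no new data. If there is no stage difference, the loss of power is trivial.

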#### 4.4.8 Randomization

Randomization of subjects will be performed using randomized blocks to keep groups as equal in numbers as possible and to avoid early filling of one of the groups. An independent randomizer that is not affiliated to the protocol will perform the randomization of subjects.

### 4.5 Relationship to other protocols

Potential participants do not have to enroll or participate in any other protocol in order to participate in this study.

This study is related to a number of other protocols and projects. The Center for Neuroscience and Regenerative Medicine (CNRM) is a collaborative intramural federal program involving the United States Department of Defense (DoD) and the National Institutes of Health (NIH). It joins clinicians and scientists across disciplines to catalyze innovative approaches to traumatic brain injury (TBI) research.

The Uniformed Services University of Health Sciences (USUHS) heads the operation of the CNRM (www.usuhs.mil/cnrm).

CNRM initially provided Henry Jackson Foundation staff and equipment to NIH through a CRADA. These staff included several providers who perform the assessment instruments. All providers are credentialed at the Clinical Center for work at NIH.

The CNRM Informatics Core was created to store all imaging and clinical data from CNRM-related protocols. All clinical data will be coded and have personally identifying material removed prior to transfer to CNRM.

Research data from neuropsychological assessments, balancing and imaging performed within the past 3 months under other CNRM studies may be included as baseline assessments in this study. This is to avoid patient burden and practice effects. Research data from the same subject may also be shared directly with CNRM investigators in protocol 10-CC-0118 (Long-term Clinical Correlates of TBI: Imaging, Biomarkers and Clinical Phenotyping Parameters) and 11-N-0084 (Evaluation and Diagnosis of Potential Research Subjects with Traumatic Brain Injury).

# 4.6 End of participation

Subjects will remain under the care of their own providers for the duration of the study. Any incidental findings on brain images, laboratory or other assessment that may require further evaluation or may impact the subjects medical care will be recorded in the medical record and shared with the subject and their health care providers at subjects' request. However, this study does not provide treatment and does not replace any therapy that a subject may be receiving as part of standard medical care for TBI.

There is one questionnaire that indicates the presence of depression. If any question about suicidal ideation is answered in the affirmative, the study physician will talk with the patient and call in the NIH staff psychiatrist if there is a concern about the patient's stability and safety. NIH policy will be followed concerning a patient who may be a danger to him/her self.

# 5. Management of Data and Samples

### 5.1 Storage

The CNRM GUID is a number assigned by the CNRM Informatics Core. The Informatics Core has established an encrypted system and will provide access to the site for generation of a GUID, developed locally at each site, from personal health identifiers (PHI) data. Only the local site will have access to PHI. Local sites will maintain Master Keys matching GUIDs to PHI. Electronic/computer Master Keys will be kept on password protected terminal(s) in locked rooms with access limited to designated study personnel.

Electronic Master Key records will be backed up electronically at each site at least monthly. Physical print outs/copies of Master Keys will be kept in a locked cabinet in the office of a designated study investigator, and will be updated monthly or at more frequent intervals. The mapping from PHI to GUID will not be stored by or known to the CNRM Informatics Core or NIH CIT personnel, but the central registration of issued GUIDs will help ensure uniformity of identifiers across sites and the ability to identify the enrolling site.

Subjects receiving follow up visits will retain initially-assigned GUIDs throughout their participation and all data will be stored linked to this GUID. Requirements or requests for

subject future contact (re-identification) must pass through the enrolling site for GUID-PHI Master Key deciphering. CNRM Master Keys will contain the following information: GUID, last name, last 4 digits SSN, date of birth, and/or medical record number.

All subjects' data will be coded and kept on password-protected computers or files in locked offices with access only by study personnel. Clinical data collected while at NIH will be coded and kept in locked cabinets. Data will also be stored using an electronic data capture system such as the NICHD Clinical Trials Database (CTDB), which is backed-up and password protected for acccess by pertinent research members. The CNRM Informatics Data Repository will provide for the CTDB data to be periodically transferred to NIH CIT, where the data repository is to be housed. Only study investigators and those associated with this protocol will have access to the samples and data. Any loss or destruction of saved data or samples will be reported to the IRB. The CNRM Informatics Core was created to store all imaging and clinical data from CNRM-related protocols. All clinical data will be coded and have personally identifying material removed prior to transfer to CNRM.

Blood samples will be transported and immediately analyzed or stored in NINR secure freezers at the NIH Clinical Center until they are ready for batch analysis. Participant names and identifying information will be removed and the samples will be assigned codes. The key to the code will be kept in a separate, secure area. NINR will be responsible for the samples at NIH.

Any samples not analyzed will be stored in the CNRM Biospecimen Repository which is operated under USUHS Protocol No. CNRM-004 "Biorepository and Informatics Warehousing". The samples will be stored at the CNRM Biospecimen Repository and deidentified and stored there for the future measurements. Blood samples will be stored in secured freezers at the CNRM Biospecimen Repository. The subject's name and identifying information will not be on the samples; they will be assigned a code. The samples will be stored for up to 20 years. The purpose of the repository is to store a large number of samples and related data so that we can learn more about traumatic brain injury and how to rehabilitate people who may have it. The CNRM is a federal medical research program of the U.S. Department of Defense (DOD), and DOD is the custodian of the samples. The Uniformed Services University operates the CNRM and the USUHS IRB reviews the repository for patient protection and receives reports from a Biorepository Steering Committee on the operations of the repository.

Before sending blood samples, we will remove the subject's name and identifying information; we will assign them a code. The key to the code will be kept in a separate, secure area. Once the samples and the code arrive at the CNRM Biospecimen Repository, a repository manager will be responsible for maintaining the samples and sending them to others who may use the samples for research. Subject's blood samples will only be accessible by current and future CNRM Investigators after approval by all relevant IRBs.

